7. PLANNED ANALYSIS

All analyses in this study are descriptive.

For categorical variables summary tabulations of the number and percentage within each category (with a category for missing data) of the parameter will be presented. For continuous variables number of values, mean, standard deviation, minimum, median, maximum and number of missing values will be presented. Incidence rates and 95% CI will be given when appropriate.

7.1 DEMOGRAPHIC AND OTHER BASELINE CHARACTERISTICS

Only descriptive statistics are planned for this section of the report. All baseline analyses will be done for the treated set.

7.2 CONCOMITANT DISEASES AND MEDICATION

Only descriptive statistics are planned for this section of the report. All analyses will be done for the treated set.

7.3 PRIMARY ENDPOINT

For the primary endpoint, the percentage of patients with therapeutic success will be presented together with the 95% confidence interval. The number and percentage of patients with and without therapeutic success will be calculated for the whole FAS set [REDACTED]

[REDACTED]

[REDACTED]

[figure not shown]
The PF-10, represented by the physical functioning subscale of the Short Form 36 (SF-36), ranges from 0 to 100. A higher score indicates a better physical functioning. The score is calculated as followed:

Answer to questions 01- 10	Score
Yes, limited a lot	1
Yes, limited a little	2
No, not limited at all	3

Transformed scale = [(Sum of final item values – 10) * 100] / 20

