9.7.2 Null and alternative hypotheses

No formal hypothesis testing will be performed since this is a self-controlled study.

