9.7.3 Planned analyses

All patients who have received at least one dose of Spiolto® Respimat® will be included in the analysis; this is the treated set. All analyses will be performed on the treated set (as-treated analysis). If patients have missing values for an outcome, those patients will be excluded for that outcome's analysis.

The assessment will be carried out using SAS® software. The statistical characteristics presented in the end-of-text tables will be N / mean / SD / min / median / max for continuous variables. Tabulations of relative and absolute frequencies will be presented for categorical variables. Incidence rates and 95% CI will be given when appropriate.

The analyses will relate to the following data as recorded in the eCRF:

- Patient demographics (age, gender, height, and weight)
- Comorbidities
- COPD related and other concomitant medication
- History of smoking
- Reported exacerbations
- Breathlessness based on mMRC score
- Physical Functioning based on PF-10 scores (therapeutic success at visit 2); primary outcome
- Changes from visit 1 to visit 2 in the PF-10 score; secondary outcome
- Patient satisfaction with Spiolto® Respimat® at visit 2 only; secondary outcome
- General condition of the patient: evaluated by the physician (Physician's Global Evaluation (PGE)); secondary outcome
- Adverse Drug Reactions (ADR & SADR), fatal AEs, pregnancies
- GOLD spirometric classification (1,2, 3, 4)
- GOLD patient groups (A, B, C, D)
- Details of treatment with inhaled respiratory agents before the study
- Details of treatment with respiratory agents during the study

- Reasons for ending treatment during the observation period
- Details of treatment continuation / discontinuation

Main analysis

For the primary outcome, the proportion of patients with therapeutic success will be presented together with the 95% confidence interval.

Further analyses

The patient's general condition (PGE) at visit 1 and visit 2, mMRC at visit 1 and patient satisfaction at visit 2 are categorical variables so they will be analyzed as tabulations of frequencies. Change from visit 1 to visit 2 in the PF-10 score is a continuous outcome, so it will be analyzed with N / mean / SD / min / median / max.

The safety data will be reported according to local requirements.

As similar studies will also be performed in other European countries, data pooling might be considered at the end.

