1 very dissatisfied 	2 dissatisfied 	3 rather dissatisfied 	4 neither satisfied nor dissatisfied 	5 rather satisfied 	6 satisfied 	7 very satisfied 
--	---	---	--	---	--	---

How satisfied are you with inhaling from the Respimat® device?

1 very dissatisfied 	2 dissatisfied 	3 rather dissatisfied 	4 neither satisfied nor dissatisfied 	5 rather satisfied 	6 satisfied 	7 very satisfied 
--	---	---	--	---	--	---

How satisfied are you with the handling of the Respimat® inhalation device?

1 very dissatisfied 	2 dissatisfied 	3 rather dissatisfied 	4 neither satisfied nor dissatisfied 	5 rather satisfied 	6 satisfied 	7 very satisfied 
--	---	---	--	---	--	---

4. Physicians' Global Evaluation (PGE) to be used directly within the eCRF

General condition of the patient at the initial examination (Visit 1)

Please mark with a cross as applicable

Poor
1 **2**

Satisfactory
3 **4**

Good
5 **6**

Excellent
7 **8**

General condition of the patient after approximately 6 weeks of treatment (Visit 2)

Please mark with a cross as applicable

Poor
1 **2**

Satisfactory
3 **4**

Good
5 **6**

Excellent
7 **8**

APPROVAL / SIGNATURE PAGE

Document Number: c03680587

Technical Version Number: 1.0

Document Name: clinical-trial-protocol

Title: Assessment of physical functioning and handling of Spiolto Respimat in patients with chronic obstructive pulmonary disease (COPD) requiring long-acting dual bronchodilation in routine clinical practice.

Signatures (obtained electronically)

Meaning of Signature	Signed by	Date Signed
Approval-Pharmacovigilance Representative		16 Nov 2015 16:32 CET
Author-Clinical Project		16 Nov 2015 16:33 CET
Approval-Team Member Medicine		16 Nov 2015 16:59 CET
Approval-Clinical		16 Nov 2015 17:30 CET
Author-Trial Statistician		16 Nov 2015 19:12 CET
Approval-On behalf of [REDACTED] or [REDACTED] or [REDACTED]		18 Nov 2015 16:06 CET
Approval-Team Member Medicine		18 Nov 2015 16:24 CET

(Continued) Signatures (obtained electronically)

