5.2 SECONDARY ENDPOINT(S)

- Absolute changes in PF-10 score from visit 1 to visit 2
- General condition of the patient, evaluated by the physician (PGE score) at visit 1 and visit 2
- Patient satisfaction with Spiolto® Respimat® at visit 2

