7.4 SECONDARY ENDPOINT(S)

All analysis will be descriptive and will be performed on FAS. For general condition of patients and patient's satisfaction with Spiolto® Respimat®, the number and percentage of patients within each category will be displayed. For absolute changes in PF-10 score, summary statistics will be provided.

[figure not shown]

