10. HISTORY TABLE

Table 10: 1 History table

Version	Date (DD-MMM-YY)	Author	Sections changed	Brief description of change
Draft v1.0	27-JUL-2016		None	This is the first Draft-Version of TSAP without any modification
Draft v1.1	11-AUG-2016		4-8	This is the second Draft-Version of TSAP. Besides adjustments in [REDACTED] analyses sets, documentation of AE was adapted
Draft v1.2	17-AUG-2016		7.3, 7.4, 8	This is the third Draft-Version of TSAP. Besides adjustments in planned statistical test, references were added
Draft v1.3	29-SEP-2016		3, 6.2, [REDACTED] 8	This is the fourth Draft-Version of TSAP. References have been updated.
Draft v1.4	14-OCT-2016		6.2	This is the fifth Draft-Version of TSAP. Display of ECadapted
Draft v1.5	19-OCT-2016		7.3, 7.4	This is the sixth Draft-Version.
Draft v1.6	21-OCT-2016		7.4	This is the seventh Draft-Version. Pooling of PGE and Satisfaction was added.
Draft v1.7	31-OCT-2016		7.4	This is the seventh Draft-Version.
Final 1.0	22-NOV-2016		[REDACTED]	[REDACTED]
Final 1.1	29-May-2017		3, 4	This is the first modification of the final version. References to CTP and TSAP were corrected

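### Does the plan need a count of patients who worsened on PF-10 and a within-patient PGE shift table to be sound?

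*SAP*

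**What the plan says.** The primary endpoint is a PF-10 gain of 10 points between the two visits (SAP 5.1; Protocol 9.1.1). SAP 7.3 reports the success percentage with a 95% CI, and: "The number and percentage of patients with and without therapeutic success will be calculated for the whole FAS set". In the public copy a redaction follows this sentence directly, with further redacted blocks after it.

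SAP 5.2 lists as a secondary endpoint "Absolute changes in PF-10 score from visit 1 to visit 2". SAP 7.4 gives it summary statistics, and SAP 7 says what these are: "For continuous variables number of values, mean, standard deviation, minimum, median, maximum and number of missing values will be presented". Protocol 9.7.3 plans the same summary apart from the count of missing values.

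For PGE and satisfaction, SAP 7.4 says that "the number and percentage of patients within each category will be displayed". Protocol 9.7.3 says that PGE at both visits, mMRC and satisfaction "are categorical variables so they will be analyzed as tabulations of frequencies". The PGE endpoint is worded as the score at visit 1 and at visit 2 (SAP 5.2), as is the objective (Protocol 8.2).

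Protocol 9.7.2 states: "No formal hypothesis testing will be performed since this is a self-controlled study". SAP 7 describes every analysis as descriptive.

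**The concern.** The patient's own baseline is the only comparator, and the headline uses it in one direction. A 50% success rate reads differently beside 2% worsened than beside 20% worsened.

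The threshold is also low in terms of answers. One category step on one item is worth 100/20 = 5 points (formula in Protocol 9.3), so success is a net gain of two steps over ten items. Ordinary two-way variation in answers produces some gainers and some losers, and the visible text counts only the gainers.

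PGE has a similar feature. The same patient is rated twice, yet the two ratings are tabulated separately, so the numbers improved, unchanged and worsened cannot be read off. At stake would be a favourable headline without the figure that puts it in proportion.

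**Working it through.** **The plan's own figure.** Protocol 9.5 assumes 50% success in 6510 patients. The half-width is 1.96 × √(0.5 × 0.5/6510) = 1.21 points, which gives 48.8% to 51.2% as stated. 7000 × 0.93 = 6510, so the drop-out allowance agrees. Nothing in the concern touches these figures. Apart from 50% and 6510, every input below is an assumption.

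**Could chance fluctuation pass unnoticed?** Let each of ten items move up one step with probability q, down one step with probability q, and otherwise stay, independently and with no true change. The SD of the score change is 5 × √(20q).

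| q | success by chance (same share loses ≥ 10) | SD of change | 95% half-width of mean change, n = 6510 |
|---|---|---|---|
| 5% | 5.9% | 5.0 | 0.12 |
| 10% | 13.5% | 7.1 | 0.17 |
| 15% | 18.9% | 8.7 | 0.21 |
| 20% | 22.5% | 10.0 | 0.24 |

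The last column is 1.96 × SD/√6510, with √6510 = 80.7. The planned mean change would sit at 0 within about a quarter of a point. The reader can form this interval from the planned N, mean and SD. The scenario behind the concern would therefore show in a summary that is already planned.

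**Do the planned PF-10 summaries fix the worsened share?** They do not. With 50% success and mean change 7.5, the limits for the share at −10 or below, over distributions on the 5-point grid from −100 to 100, are:

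| SD | any shape | single-peaked | normal, cut at −7.5 |
|---|---|---|---|
| 10 | 0% to 19.8% | 0% to 11.0% | 6.7% |
| 15 | 0% to 39.2% | 0.2% to 21.0% | 15.9% |
| 20 | 0% to 50.0% | 2.3% to 28.4% | 22.7% |

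The any-shape limits are corner cases. At SD 15 the upper limit places 39.2% at −10, 10.8% at +5, 32.5% at +20 and 17.5% at +25, so nobody has zero change. The lower limit needs about 2% of patients to gain 100 points. The single-peaked lower limit at SD 15 needs a flat tail out to the end of the scale. If all changes lay within ±50, which the planned minimum and maximum would show, it rises from 0.2% to about 4%. The contrast of 2% with 20% worsened would then not be available at that mean and SD.

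**PGE.** Take assumed percentages Poor/Satisfactory/Good/Excellent of 20/50/25/5 at visit 1 and 10/35/45/10 at visit 2. Numbering the labels 1 to 4, the means are 0.20 + 1.00 + 0.75 + 0.20 = 2.15 and 0.10 + 0.70 + 1.35 + 0.40 = 2.55, so the net shift is 0.40 label. With moves of at most one label, these tables fit two extremes:

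- 40% improved (10% + 25% + 5%), 60% unchanged, 0% worsened;
- 70% improved (20% + 40% + 10%), 0% unchanged, 30% worsened (10% + 15% + 5%).

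The difference between improved and worsened is 40 points in both, and the two planned visit tables give the net shift. The second extreme requires that no patient keeps the same label over six weeks. The example also reduces an eight-box scale (Protocol 9.4 and Annex 3) to its four labels.

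**Against the objectives (Protocol 8.2).** The primary objective is to measure change in physical functioning. The success rate with its CI and the two-directional change summary answer it. The secondary objective is general condition at visit 1 and at visit 2. Frequencies at each visit answer it.

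**The case for a change.** The best argument for the concern is that the mean does not determine how many patients declined. That is true, and the ranges above confirm it: the minimum shows only the worst patient, and two visit tables do not give individual PGE changes. In a descriptive study the tables are the whole evidence. The two extra displays need no new data and would be precise. At n = 6510 with 50% success and 7% to 27% worsened, the half-width would be 0.6 to 1.1 points for the worsened share and 1.5 to 2.1 points for improved minus worsened.

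This makes the displays informative, not necessary. Improved minus worsened is a second net measure beside the mean change, and the plan already has the first. What is left is the gross share of decliners, which no stated objective or endpoint asks for and which can be tabulated later from the same data.

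A second argument is that Protocol 9.7.3, which is unredacted, mentions neither table, and that SAP 4 declares only the new analysis set as a change. That stands at protocol level. It does not settle the SAP, because the sentence in 7.3 runs straight into redacted text, where a further split of the primary endpoint could sit. The SAP history table also records for section 7.4: "Pooling of PGE and Satisfaction was added". No such pooling is visible there now. It may have been dropped or it may be hidden. Pooling categories is not in itself a within-patient split, but the entry means that the visible 7.4 cannot be assumed complete.

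**Conclusion.** The concern does not hold. Followed as written, the plan gives the success rate with a 95% CI, a summary of PF-10 change that takes in losses as well as gains, and PGE frequencies at both visits. These match the stated objectives and endpoints and support the descriptive conclusions the study can draw. If success came from fluctuation alone, the mean change would be about 0, with a half-width of at most about 0.24 points in the cases examined.

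What remains true is narrow: the visible text does not report the share losing 10 or more points, and the planned summaries leave it open (0.2% to 21% for single-peaked shapes at an assumed mean of 7.5 and SD of 15, or about 4% to 21% if changes stay within ±50). Showing it, with a PGE shift table, is a matter of reporting preference. It would alter neither the primary estimate and its interval nor the study size. Whether the tables are absent at all cannot be determined from the redacted SAP.

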7.4 SECONDARY ENDPOINT(S)

All analysis will be descriptive and will be performed on FAS. For general condition of patients and patient's satisfaction with Spiolto® Respimat®, the number and percentage of patients within each category will be displayed. For absolute changes in PF-10 score, summary statistics will be provided.

[figure not shown]

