9. RESEARCH METHODS

9.1 STUDY DESIGN

This is a self-controlled study design enrolling consented COPD patients who will be treated with Spiolto® Respimat® according to the approved SmPC.

Patients will be enrolled consecutively and will be followed over an observational period of approx. 6 weeks. Data as listed in table 9.1:1 will be collected.

Table 9.1:1: Visit flow chart and data collection parameters

Parameter	Visit 1; baseline visit	Visit 2; approx. 6 weeks after baseline visit
Informed Consent	X	
Inclusion / Exclusion Criteria	X	
Patient demographics (age, gender, height, and weight)	X	
Start of COPD	X	
Number of exacerbations in the last 12 months	X	
Number of exacerbations leading to hospitalization in the last 12 months	X	
mMRC breathlessness scale, completed by the patient	X	
Past COPD therapies (6 months before visit 1)	X	
Respimat® training (yes/no)	X	
COPD severity based on GOLD assessment ¹	X	
Smoking status/history	X	X
Concomitant diseases / Comorbidities	X	X
COPD related and other relevant concomitant medication	X	X
Physical functioning (PF-10) questionnaire, completed by the patient	X	X
General condition of patient evaluated by Physician's Global Evaluation (PGE)	X	X
Safety: Adverse Drug Reactions (serious and non-serious), fatal AE, pregnancy	X	X
Patient satisfaction with Spiolto® Respimat®, completed by the patient		X
Rational for Spiolto® Respimat® treatment discontinuation (if applicable)		X
Continuation or discontinuation of treatment with Spiolto® Respimat® after the study (yes/no)		X

¹ GOLD patient group (A, B, C or D) will be automatically calculated within the eCRF based on available exacerbation history, mMRC, and GOLD spirometric classification of airflow limitation based on post-bronchodilator FEV₁ if available.

Baseline characteristics of patients being eligible and who gave Informed Consent, but were not treated in the study will also be collected.

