9.5 STUDY SIZE

In a previous study, 205.426 with over 1000 patients treated with Spiriva[®] Respimat[®], therapeutic success (i.e., 10-point increase in the PF-10 score between visit 1 and visit 2) was achieved in 61% of the patients.

In this study, a lower therapeutic success rate is expected as patients may be already on maintenance treatment at baseline. Assuming a 50% therapeutic success rate and 6510 patients, the 95% confidence interval for the therapeutic success rate would be between 48.8% (lower limit) and 51.2% (upper limit).

To account for a 7% drop-out rate, the sample size becomes 7000 patients.

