6.3 PATIENT SETS ANALYSED

Full analysis set (FAS): All screened patients with informed consent, date of registration, at least one documented administration of Spiolto® Respimat® and available PF-10 score at visit 1 and visit 2.

Treated set (TS): All screened patients with informed consent, date of registration and at least one documented administration of Spiolto® Respimat®.

Table 6.3: 1 Patient sets analysed

Class of endpoint	Patient set	
	TS	FAS
Primary and secondary endpoints		X
Safety endpoints	X	
Demographic/baseline	X	

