6.7 BASELINE, TIME WINDOWS AND CALCULATED VISITS

Baseline visit (Visit 1) will include historical and demographic data as well as registration and initial examination. Treatment with Spiolto® Respimat® will be documented at visit 2 after approximately 6 weeks of treatment.

The mMRC breathlessness scale is completed by the patient at visit 1 and PF-10 questionnaire at visit 1 and 2 as well as satisfaction survey at visit 2. In addition, the PGE is completed by the physician at visit 1 and visit 2.

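### The SAP restricts PGE and patient satisfaction to patients with a PF-10 score at both visits, whereas the protocol uses the treated set with exclusion outcome by outcome

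*SAP*

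**What the plan says.** Protocol 9.7.3 defines the treated set as patients with at least one dose. It then states: "All analyses will be performed on the treated set (as-treated analysis"). Its missing-data rule works by outcome: "If patients have missing values for an outcome, those patients will be excluded for that outcome's analysis". The same section lists PGE and patient satisfaction as secondary outcomes, so the rule covers them.

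The SAP defines two sets in 6.3. The treated set is: "All screened patients with informed consent, date of registration and at least one documented administration of Spiolto® Respimat". The FAS has the same conditions on consent and registration, and then requires "at least one documented administration of Spiolto® Respimat® and available PF-10 score at visit 1 and visit 2". SAP Table 6.3:1 assigns the primary and secondary endpoints to the FAS. SAP 7.4 repeats this for the secondary endpoints ("All analysis will be descriptive and will be performed on FAS") and goes on to name general condition and satisfaction.

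SAP section 4 lists the FAS as a set that the protocol does not contain and points to 6.3. No visible text explains why it should govern endpoints that do not use the PF-10.

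**The concern.** Whether a patient has a PF-10 pair says nothing about whether PGE or satisfaction was recorded. The clearest case is a patient who returns at visit 2 but has no usable PF-10 pair, because a form is absent or has five or more of its ten items blank at either visit. According to SAP 6.7, treatment with the product "will be documented at visit 2 after approximately 6 weeks of treatment". This patient can therefore have the documented administration that the SAP treated set needs, and may have PGE and satisfaction on record, yet is removed from both endpoints.

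PGE looks more exposed than satisfaction. Protocol Annex 3 has the physician enter PGE directly in the eCRF. Satisfaction is a paper form that the same patient completes at the same visit as the second PF-10, so those two may often be missing together. The documents give no missing-data rates to test this.

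At stake are the denominators of two of the three secondary endpoints. These two are also the only outcomes named in the secondary objectives (protocol 8.2).

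**Working it through.** **Which endpoints are affected**

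| Endpoint | Patients under protocol 9.7.3 | Patients under SAP 6.3 and 7.4 |
|---|---|---|
| Therapeutic success, PF-10 change | Treated, PF-10 at both visits | Essentially the same |
| PGE at visit 1 or visit 2 | Treated, PGE recorded at that visit | Also needs PF-10 at both visits |
| Satisfaction at visit 2 | Treated, satisfaction recorded | Also needs PF-10 at both visits |

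**The plan's own figures (protocol 9.5).** With 50% success and 6510 patients, the half-width is 1.96 × √(0.25/6510) = 1.21 points. The interval is 48.8% to 51.2%, as stated. For the total the protocol says: "To account for a 7% drop-out rate, the sample size becomes 7000 patients". This also reproduces: 6510/0.93 = 7000, and 7000 × 0.07 = 490.

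**Visit 2 loss.** Assumptions:
- The 7% drop-out equals the share without a PF-10 pair, so 490 lack one and 6510 form the FAS.
- r of the 490 return with the outcome recorded (r = 0, 70, 210 or 350).
- These r patients differ from the FAS by 10 to 30 percentage points in a given category.
- Percentages are taken among patients with the outcome recorded, and all FAS patients have it.

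The excluded share is r/(6510 + r). The shift in the reported percentage is that share times the difference.

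**Visit 1 PGE loss.** Assume that all 490 have a visit 1 PGE. Let f be the share of non-returners with a documented administration (not given, 0 to 1). Records lost, relative to the SAP treated set, are r + f × (490 − r).

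| r | Visit 2 share excluded | Shift at visit 2 (points) | Visit 1 PGE lost, f = 0 | f = 0.5 | f = 1 |
|---|---|---|---|---|---|
| 0 | 0 | 0 | 0 | 245 | 490 |
| 70 | 70/6580 = 1.06% | 0.11 to 0.32 | 70 | 280 | 490 |
| 210 | 210/6720 = 3.13% | 0.31 to 0.94 | 210 | 350 | 490 |
| 350 | 350/6860 = 5.10% | 0.51 to 1.53 | 350 | 420 | 490 |

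Under the 7% assumption, 490 is the upper bound on the loss at either visit. Non-returners without a documented administration fall outside the SAP treated set too, so changing the set does not recover their visit 1 PGE.

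**Why a change in PGE must be paired.** Take r = 0. An unpaired comparison on the treated set includes non-returners at visit 1 only. The distortion is f × 490/(6510 + f × 490) times their assumed 10 to 30 point difference at visit 1:
- f = 0: none.
- f = 0.5: 245/6755 = 3.63%, or 0.36 to 1.09 points.
- f = 1: 490/7000 = 7%, or 0.7 to 2.1 points.

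Restricting the comparison to patients with PGE at both visits removes this distortion.

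**The case against.** The strongest reply is that the change is disclosed. SAP section 4 names the FAS, Table 6.3:1 shows where it applies, and protocol 9.7.1 leaves details to the analysis plan. One common set for all efficacy tables is a defensible choice, and the study is descriptive with no hypothesis test. Disclosure does not, however, explain why PF-10 completeness should decide who counts for PGE and satisfaction.

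Several limits do stand:
- Parts of the SAP are blacked out or not shown (a contents entry between 6.3 and 6.5, parts of 7.3, a figure at 7.4, entries in the history table). A reason may be there.
- SAP section 7 already asks for a missing-data category in categorical tables. If missing values enter the percentage denominator, the shifts above do not apply as calculated. The visible text does not settle this.
- The two treated sets are not identical. The protocol asks for one dose received; the SAP asks for a documented administration and a registration date. Non-returners may meet the first and fail the second.
- For comparing PGE between visits, the FAS already leaves out most patients seen only at visit 1. Pairing on PGE does this without also dropping returners who lack a PF-10.
- The values of r, f and the 10 to 30 points are assumptions. If no patient without a PF-10 pair has visit 2 data, the visit 2 effect is zero.

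**Conclusion.** The concern holds. The two documents select different patients for PGE and satisfaction, and the SAP, followed as written, discards valid records of both. That difference is certain from the text. The absence of a reason is certain only for the visible text. The effect on visit 2 percentages is probably small: 0 to about 1.5 points under the assumptions above, with direction unknown. Visit 1 PGE could lose up to 490 records if 7% lack a PF-10 pair. For scale only, the planned half-width for the primary endpoint is 1.2 points; no precision target is stated for PGE or satisfaction. Therapeutic success and PF-10 change are unaffected. The point should be corrected because the correction is cheap, but it does not threaten the main result.

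**What to change.** - In SAP Table 6.3:1 and section 7.4, assign PGE and satisfaction to the treated set, using all patients with that outcome as protocol 9.7.3 provides. Show the number missing in each table and say whether missing values enter the percentage denominator.
- Base any comparison of PGE between visit 1 and visit 2 on patients with PGE at both visits.
- Keep the FAS for therapeutic success and PF-10 change.
- Record this assignment in SAP section 4.

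The cost is one row in the table, one or two sentences in each of sections 4 and 7.4, and one additional paired PGE table. No new data are needed. The drawback is that denominators will differ by endpoint, so each table must show its own.
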